### **Statistical Analysis**

The results of the statistical analysis will be expressed as mean  $\pm$  standard deviation (SD) or median and interquartile range (IQR). The comparison analysis of the results will be obtained from ambulatory spirometry and results from home spirometry using the AioCare spirometer will be performed using paired, parametric Student t-test, or non-parametric Wilcoxon signed-rank test (depending on whether compared values were normally distributed, which was evaluated using the Shapiro–Wilk test) with a significance level of  $p = 0.05$ .

The relationship between the compliance of spirometry parameters, such as number of days with performed spirometry tests and clinical parameters (age, BMI, AS, VS, BS) and spirometry results (FEV1%pv or FVC%pv), will be evaluated using linear regression analysis. The goodness of fit of the model, based on Akaike's information criterion (AIC), will be compared between the four models. The number of independent variables will be reduced using backward, stepwise regression models. This method allows for a decrease in the variables from the model that do not contribute to the explanation of the variability of dependent variables, which reduces the complexity of the model (which was necessary due to the limited sample size). The correlation between continuous variables will be evaluated using Pearson correlation coefficients.

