Implementation of the above-mentioned tests often encounters difficulties which increase when the child loses independent walking. Additionally, during the COVID pandemic, which runs from March 2020 in Poland, spirometry was included in the procedures generating aerosols, i.e. high risk of SARS-CoV-2 virus transmission. Therefore, it has become necessary to look for other methods of measuring and monitoring lung function in children with DMD.

Because a major component of respiratory dysfunction seems to be decline of inspiratory muscle weakness [3,6] therefore also respiratory training and rehabilitation is recommended as one of the key elements of DMD patient care [1,3].

The time of the SARS-CoV-2 pandemic also makes it necessary to look for rehabilitation methods at home. The assumption of the exercises is the possibility of performing them independently, at home, without the assistance of a physiotherapist, and without the use of additional equipment.

Summary: Pulmonary rehabilitation is one of the key issues in DMD patient management. The combination of systematic home lung function measurement with home respiratory rehabilitation is an innovative project. It is a non-invasive test, and the measurement is intended to improve the quality of life of DMD patients.

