### **3. AIMS, OBJECTIVE**

**Objectives:**

The primary objective of this study is to evaluate whether using home electronic device to monitoring pulmonary function and/or home telerehabilitation can slow the rate of progression pulmonary function in males with DMD compared to control group without using home e-device and telerehabilitation.

The second aim of this study is:

to investigate whether it is possible to monitor pulmonary function at home using an electronic spirometry system called AioCare in boys with DMD.

to assess the acceptance of telerehabilitation of respiratory system in this group of patients.

to assess the acceptance of electronic home monitoring of respiratory system in this group of patients.

to assessment of the quality of life of patients subjected to electronic monitoring and pulmonary rehabilitation vs. not subjected (validated questionnaires)

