MicroRPM- Maximal respiratory pressure and reflecting respiratory muscle strength was measured using a calibrated portable hand-held mouth pressure meter (MicroRPM; Micro Medical Ltd., Rochester, England) in a sitting position. To measure maximal expiratory pressure (MEP), subjects performed maximal expiratory effort after maximal inspiration. Maximal inspiratory pressure (MIP) was measured by exerting maximal inspiratory effort after maximal expiration. To measure these pressures, effort was maintained for at least 1 second. The highest positive MEP value and the lowest negative MIP value in three or more attempts were chosen. We calculated percent predicted MEP (MEP%) and MIP (MIP%) values according to the formulas: **MEP%**  $MEP * 100 / (7.619 + (7.806 * age) + (0.004 * height * weight))$ ; **MIP%**  $MIP * 100 / (-27.020 - (4.132 * age) - (0.003 * height * weight))$

- Pulmonary function tests

Lung function by spirometry using the calibrated, computerized spirometer Pneumo Screen (Jaeger, Germany) will be performed according to the European Respiratory Society and American Thoracic Society recommendations, by a certificated, experienced pediatric pulmonologist [6,14]. The highest value of forced vital capacity (FVC), forced expiratory volume in 1 second (FEV1), peak expiratory flow (PEF) expressed as liters (L) and liters per minute (L/min) accordingly, and percent predicted value (%pv) from correct acceptable attempts will be evaluated. The results will be compared with results from home electronic spirometry.

- Assessment of the muscles of the upper limb

Performance of Upper Limb (PUL)- a functional scale specifically designed for assessing upper limb function in Duchenne muscular dystrophy (DMD). It includes three domains (shoulder, mid- and distal), each including items exploring activities easily related to activities of daily living that both patients and clinicians identified as relevant. Each dimension (shoulder, mid, distal) can be scored separately. In the PUL 2.0 there is a maximum score of 12 for the shoulder level, 17 for the mid-level, and 13 for the distal level. A total score of 42 can be achieved by adding the three level scores [15].

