## **8. STATISTICAL CONSIDERATIONS**

### **Sample size estimation**

Estimation of the sample size was based on the expected differences of the FVC between the groups with and without intervention. In the reference studies annual decline of FVC is varied between 6-11% (mean 8.5%). Assuming that telerehabilitation with using mobile spirometry can decrease this decline to 6% per year with standard deviation of 3% we estimated sample size for the study arms. Taking into account 80% power of the test, 5% significant level, the number of the subjects in the arm 1 (AioCare

device spirometry + telerehabilitation of the respiratory system) and control group equals 46 per group; finally 50 subjects per group were established. The same number of subjects were determined in the rest arms of the study (arm 2 – only mobile spirometry and arm 3 – only telerehabilitation).

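### The clinic-versus-home spirometry comparison uses a paired t-test or Wilcoxon test, which looks for an average shift and does not measure how closely the two readings agree

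*Protocol*

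**What the plan says.** The Statistical Analysis part of section 8 names the method for comparing clinic and home readings. The comparison "will be performed using paired, parametric Student t-test, or non-parametric Wilcoxon signed-rank test", with a significance level of 0.05. The choice between the two tests is made "depending on whether compared values were normally distributed, which was evaluated using the Shapiro–Wilk test".

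The comparison is announced twice. Section 7.1.1 (Pulmonary function tests) says "The results will be compared with results from home electronic spirometry", and section 7.1.2 (Visit 2 and Visit 3) repeats it. It bears on a secondary aim in section 3: "to investigate whether it is possible to monitor pulmonary function at home using an electronic spirometry system called AioCare in boys with DMD". The Introduction gives the motive. Clinic spirometry is hard to carry out and became a transmission risk during the pandemic, so "it has become necessary to look for other methods of measuring and monitoring lung function in children with DMD".

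The same statistical section also mentions mean and SD or median and IQR as general output, Pearson correlation between continuous variables, and regression models for compliance. None of these is assigned to the within-pair differences between devices. The Protocol mentions no limits of agreement, intraclass or concordance coefficient, or acceptable difference.

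**The concern.** A paired t-test or signed-rank test is a test of location. It can show that home readings run higher or lower than clinic readings on average, but not how far one boy's home reading may lie from his clinic reading. For a device meant to monitor individual children, that distance is the main question. The Introduction itself ties individual FVC values (2.1 L and 1 L) to decisions about care.

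The test can also mislead in a particular direction. Its statistic divides the mean difference by its standard error, so a noisier device is less likely to be declared different. A non-significant result may reflect wide scatter, and a significant one may reflect a trivial bias with tight agreement.

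A smaller point concerns the choice between the two tests, which is made "depending on whether compared values were normally distributed". The paired t-test depends on the distribution of the differences, not of the two sets of raw readings.

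**Working it through.** The Protocol states no figure for this comparison, so there is none to reproduce. The calculations below illustrate how the stated test behaves.

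**Inputs**
- Pairs: arms 1 and 2 receive the home device (section 7.1.1). With 50 per arm and about 10% dropout, 45 per arm remain (section 1.1, Study Description), giving 90 boys. Results for 60 and 100 pairs are also shown.
- Level: 0.05 (Statistical Analysis). Sidedness is not stated; two-sided is assumed.
- SD of the home-minus-clinic differences: not given. Assumed, from 0.05 to 0.30 L.
- Scale: mean annual FVC decline of 8.5% (Sample size estimation), applied to an assumed FVC of 1.5 to 2.5 L.

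**Formulas**
- Test statistic: t = mean difference / (SD/√n)
- 95% limits of agreement: bias ± 1.96 × SD
- 95% CI half-width of each limit: t(0.975, n−1) × SD × √(1/n + 1.96²/(2(n−1)))

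**Step 1: what passes as no difference.** The observed mean difference is non-significant if it is below t(0.975, n−1)/√n SDs. This is 0.258 SD for n = 60, 0.209 SD for n = 90 and 0.198 SD for n = 100. The threshold is a multiple of the SD, so the bias that goes undetected grows with the scatter. At n = 90 it is 0.010 L when the SD is 0.05 L and 0.063 L when the SD is 0.30 L.

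**Step 2: chance of significance against actual agreement, n = 90**

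| True bias | SD of differences | P(significant) | 95% limits of agreement |
|---|---|---|---|
| 0 | 0.30 L | 5% | −0.59 to +0.59 L |
| 0.02 L | 0.10 L | 47% | −0.18 to +0.22 L |
| 0.02 L | 0.05 L | 96% | −0.08 to +0.12 L |

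For the last row, the probability is 86% with 60 pairs and 98% with 100.

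**Step 3: same observed shift, opposite verdicts.** Take an observed mean difference of 0.03 L and n = 90.
- SD 0.05 L: t = 0.03/(0.05/√90) = 5.69, p = 1.6 × 10⁻⁷, limits −0.07 to +0.13 L.
- SD 0.30 L: t = 0.03/(0.30/√90) = 0.95, p = 0.35, limits −0.56 to +0.62 L.

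The device with far worse agreement is the one not found to differ.

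**Step 4: scale.** One year's mean decline is 8.5% × 1.5 L = 0.128 L to 8.5% × 2.5 L = 0.213 L. Limits of ±0.588 L equal 0.588/0.213 = 2.8 to 0.588/0.128 = 4.6 years of decline. The upper limit of 0.118 L for the tight device is less than one year's decline. With limits of ±0.588 L, a boy at 2.1 L in the clinic could read anywhere from about 1.51 to 2.69 L at home.

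**Step 5: precision of the alternative.** The half-width of each limit's confidence interval is 0.36 SD with 90 pairs and 0.44 SD with 60. At n = 90 this is ±0.02 L for an SD of 0.05 L and ±0.11 L for an SD of 0.30 L.

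**Step 6: the normality rule.** In a simulation with n = 90 and 4,000 runs, FVC was assumed skewed (0.3 L plus a gamma variable with shape 4 and scale 0.45 L) and the differences normal with SD 0.15 L. Shapiro–Wilk rejected on the raw FVC values 94% of the time and on the differences 5% of the time.

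**The case against.** The aim in section 3 is worded as feasibility and sets no explicit accuracy or interchangeability objective. Usability and adherence are covered by the satisfaction survey at Visit 1 and by the compliance regression. This limits the reach of the point but does not remove it: the Introduction looks for another way to measure lung function, and the Protocol twice commits to comparing the two devices.

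An SAP that is not shown could add an agreement analysis, and margins, confidence intervals and the handling of repeated visits are often left to it. That is fair for those details. The Protocol is not silent on the method, however. It names a location test, and that choice would still need correcting. The general descriptive statistics and the Pearson correlation do not fill the gap: two devices that differ by a constant 0.5 L would correlate perfectly.

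The assumed SDs are illustrative, and the intermediate case in the table is less stark. The Protocol plans three correct home measurements twice daily and does not say which home value is paired with a clinic value; averaged home readings might scatter less. The figure of 90 also applies a 12-month dropout rate to comparisons announced for earlier visits. These objections affect the size of the example, not the direction of the effect, which follows from the form of the t statistic.

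The normality point is minor. If raw values are tested, the usual consequence is more use of the Wilcoxon test, which loses only about 5% efficiency when the differences are normal. Nothing in the Protocol says that a non-significant result will be read as equivalence, but it offers no other basis for a conclusion.

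**Conclusion.** The concern holds. The named method can detect an average shift between clinic and home spirometry but cannot show whether the readings agree closely enough for home monitoring. Under the assumed SDs and 90 pairs, a device with limits of agreement of ±0.59 L would be non-significant 95% of the time, while one with limits of −0.08 to +0.12 L would be significant 96% of the time. The litre values and the years-of-decline scale depend on the assumed SDs and FVC. The reversal does not: it is a property of the test.

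The consequence is confined to the accuracy side of one secondary aim. The primary between-arm comparison, the survey and the compliance regression are unaffected. The change should be made, but it does not threaten the trial's main result.

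**What to change.** Reword the Statistical Analysis section so that the main analysis of clinic against home spirometry, for FVC and FEV1, is the mean home-minus-clinic difference and the 95% limits of agreement, each with confidence intervals. State in advance the difference that would be acceptable, and judge the limits against it. Define which home readings are paired with each clinic value, and allow for repeated visits per boy. Keep the paired test, if wanted, only as a description of bias, and apply any normality check to the differences.

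This is a change of wording and needs no extra data or patients. The planned numbers give adequate precision for the limits. The one real task is to agree the acceptable difference before the data are examined.

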**Study Description:**

The controlled and observational 12-months study with prospective cohort design and longitudinal data collection performs in paediatric patients with established diagnosis of DMD, at the Department of Allergy and Pulmonology Medical University of Gdansk, Poland.

The study includes 200 patients with DMD diagnosis confirmed by genetic testing, 7-17 years old (7  $\geq$  and  $<$ 18) at the study entry with the routine standardized a follow-up of up to 4 weeks, 12 weeks, 24 weeks and 12 months.

The study size is estimated at 200, with a dropout rate after the 12-month follow-up period being ca. 10% (N=180). The study consists of 4 arms: 3 actives and 1 control (each arm of n=50 participants; with dropout rate after 12 months ca.10%, n=45).

Duration of the project March 2021 - March 2025.

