## 7. STUDY INTERVENTION

### 7.1 Description of all Trial Periods

#### 7.1.1. Enrollment visit

During the enrollment visit, medical history data and clinical symptoms of the respiratory system will be collected from an interview. A physical examination, Vignos scale (VS) assessment, Brooke scale (BS) assessment, and spirometry (Jaeger, Germany), Respiratory muscle assessment (Maximal inspiratory pressure -MIP, and Maximal expiratory pressure- MEP), Assessment of the muscles of the upper limb (Performance of Upper Limb -PUL), Maximal grip strength (dynamometry) will be performed in all participants.

**Participants on arm 1 and 2 will receive an electronic individual spirometer (AioCare) with a 2-h training session how to use it. Each participant was then asked to perform on their own three correct spirometry measurements twice daily (morning and evening) at home.**

**Participants from arm 2 and 3 will receive a 1-hour training with respiratory rehabilitation and link to video presentation with respiratory rehabilitation exercises to home daily using.**

- Functional status

The functional status of the participants was assessed by the Vignos scale (VS). The scores on the VS range from 1 to 10 (1 - the subject can walk and climb stairs without assistance, 10 - the subject is

confined to a bed). The VS allows staging of the disease and focuses on functional ambulatory activities. This is the main scale used for characterizing the progression of disease [12]. Upper limb functional status was assessed with the 6-point Brooke scale (BS) (1 - the subject can abduct their arms in a full circle until they touch above their head, 6 - the subject has no useful function of the hands) [13].

- Respiratory muscle assessment

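### The home-spirometry compliance regression uses backward stepwise selection for a sample-size reason that does not hold, and so will exaggerate the predictors it keeps

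*Protocol*

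**What the plan says.** Protocol section 8, Statistical Analysis, plans a linear regression relating "compliance of spirometry parameters, such as number of days with performed spirometry tests" to "clinical parameters (age, BMI, AS, VS, BS) and spirometry results (FEV1%pv or FVC%pv"). Goodness of fit by AIC "will be compared between the four models", which are not defined. Then: "The number of independent variables will be reduced using backward, stepwise regression models". The reduction in complexity is explained as something "which was necessary due to the limited sample size".

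The section gives no removal threshold for the backward step and no shrinkage, validation or correction for selection. It does not call the analysis exploratory.

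Two other places fix the sample available. Section 7.1.1: "Participants on arm 1 and 2 will receive an electronic individual spirometer (AioCare"). The Study Description in section 1.1: "each arm of n=50 participants; with dropout rate after 12 months ca.10%, n=45".

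**The concern.** Backward selection uses the data to choose the variables and then reports the chosen model as if it had been fixed beforehand. A variable survives more easily when its estimate is large by chance, so surviving coefficients are biased away from zero, and their ordinary standard errors and p-values take no account of the choice. A small sample makes this worse, so even a valid small-sample argument would be a poor reason for stepwise selection.

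At stake is the only multivariable analysis of compliance in the Protocol. A noise variable, or a weak one made to look strong, could be reported as a determinant of which boys keep up home spirometry. The candidates are likely to be correlated: the Introduction ties lung function to age and loss of walking, and the Vignos and Brooke scales grade the same disease. With AIC removal, correlation makes false p<0.05 findings more frequent.

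**Working it through.** The Protocol states no sample-size figure for this regression, so there is none to reproduce. The check has two parts.

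**1. Is the sample too small for the full model?**

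Inputs: two arms with a device (7.1.1); 50 per arm, about 45 after dropout (Study Description); five clinical variables plus one spirometry measure, so 6 candidates, or 7 if FEV1%pv and FVC%pv both enter (Statistical Analysis).

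- Pooled n: 2 × 50 = 100 enrolled; 2 × 45 = 90 at 12 months.
- Boys per candidate: 90/7 = 12.9; 90/6 = 15.0; 100/7 = 14.3; 100/6 = 16.7.

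A linear model with 6 or 7 terms can be fitted to 90 boys without selection. In simulation the full model's 95% intervals cover 94.7-95.2% at n=90 to 100.

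**2. What does selection do?**

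Assumptions, since the Protocol gives none: normal data, equal pairwise correlation between candidates, and two possible removal rules, p>0.05 or AIC. For one variable, AIC removal corresponds roughly to a p threshold of 0.157.

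Analytic check for k independent null candidates, P(at least one) = 1 − (1 − α)^k:

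- k=6, α=0.05: 1 − 0.95^6 = 26.5%. k=7: 30.2%.
- k=6, α=0.157: 1 − 0.843^6 = 64.1%. k=7: 69.7%.

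Simulation, n=90, 6 candidates, all null, 2,500 runs per row:

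| Rule | Correlation | At least one kept | Any p<0.05 after selection | Any p<0.05, full model |
|---|---|---|---|---|
| p>0.05 | 0 | 27.0% | 27.0% | 25.4% |
| p>0.05 | 0.3 | 26.6% | 26.6% | 24.5% |
| p>0.05 | 0.6 | 27.8% | 27.8% | 24.5% |
| AIC | 0 | 66.5% | 28.2% | 25.7% |
| AIC | 0.3 | 68.6% | 34.3% | 26.9% |
| AIC | 0.6 | 68.5% | 40.2% | 23.6% |

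With 7 candidates at correlation 0.3, the p rule gives 31.3% against 28.0% for the full model. AIC keeps something in 71.3% and shows a p<0.05 in 37.3%, against 27.6%. Over all settings tried with 6 or 7 candidates, AIC leaves at least one variable in about 66-75% and at least one p<0.05 in about 28-45%; the p rule gives 26-34%; the unselected model gives 23-31%.

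Effect on real predictors:

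- One true standardised slope of 0.10, correlation 0.5, n=90: mean estimate when kept is 0.21-0.28 across the two rules, or 2.1 to 2.8 times the truth. The nominal 95% interval covers about 69-79%. The p>0.05 rule lies at the worse end of both ranges. The full model covers about 95%.
- Two true slopes of 0.2, six candidates, correlation 0.3 or 0.6, n=90: coverage over all kept variables is 68% or 48% under the p rule and 81% or 71% under AIC. The full model stays at about 95%.

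**The case against.** **The removal rule is unknown.** This stands. AIC is named only for comparing the four models, so the 66-75% figure is conditional on an assumption. If removal is at p>0.05, selection adds little to the rate of chance findings. Exaggeration and under-coverage remain under both rules.

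**Much of the false-positive rate is multiplicity.** This also stands. A reader might set 28-45% against the roughly 5% of an overall F-test and blame the whole gap on stepwise selection. The like-for-like figure is any p<0.05 in the unselected model, 23-31%. In the table the excess under AIC runs from 28.2 − 25.7 = 2.5 points at correlation 0 to 40.2 − 23.6 = 16.6 points at 0.6. Under the p rule it is about 2 to 3 points.

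**The regression is a side analysis.** Largely right. A reader might infer that it is the only analysis of feasibility. It is not: the same section plans paired comparisons of home with clinic spirometry and Pearson correlations, and section 7.1.2 plans a survey of compliance, satisfaction and obstacles. Section 3 asks whether home monitoring is possible, and lists no objective about predictors of compliance.

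**The sample may really be limited.** If any of the four undefined models is fitted within one arm, 45 boys give 45/7 = 6.4 to 45/6 = 7.5 per candidate. The Protocol does not say that this is intended, and selection would be less stable there, not more.

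**No intervals are promised.** True: the section mentions none for this regression. That limits the coverage argument, but the bias in the coefficients does not depend on it. Reporting detail may lie in a SAP; the selection method and its reason are fixed here.

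**Conclusion.** The point holds for a secondary analysis, and its weight is modest. The stated reason for dropping variables is not borne out by the Protocol's own numbers when the two device arms are pooled with recruitment as planned. Under either common removal rule, the variables that survive will look stronger and more certain than they are. A marked rise in chance predictors depends on AIC removal and on correlated candidates, neither of which the Protocol states.

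The size rests on simulated normal data with equal correlations, so the figures are indicative. Nothing here touches the between-arm FVC comparison. The past tense of the justification might suggest text carried over from a finished, smaller study, but the document does not establish that and the point does not need it.

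**What to change.** In section 8, Statistical Analysis:

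- Drop the stepwise step. Fit one pre-specified linear model on arms 1 and 2 pooled, with the listed clinical variables and one spirometry measure chosen in advance.
- Define AS, which is missing from the abbreviations list, or remove it.
- Report all coefficients with 95% confidence intervals and an overall F-test of the set. The F-test is needed because individual p-values in the full model still carry multiplicity (23-31% for at least one false p<0.05).
- Label the analysis exploratory, and delete the small-sample justification. With a single model, the AIC comparison of four undefined models has no further role.

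The cost is wording only, with no extra boys, visits or data. The downside is a less compact model with wider intervals, more so if age, VS, BS and the spirometry measure are strongly correlated.
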